Table 4 shows the statistical power to detect various incremental increases in R² due to the addition of change in serum urate in various regression models. For example, 92 individuals will provide 87% power using a Type I error rate of 0.05 to detect an increase of 7.5% in R² by adding change in serum urate to a regression model that already explains 20% of the variability in the change in BP with 5 control variables (age, sex, race/ethnicity, body mass-index, glomerular filtration rate). Due to the nature of multivariable linear regression, identical results hold for changes in hsCRP and FMD.

I. Risks and discomforts

1.Risks associated with phlebotomy

Subjects may experience pain from the needle used during phlebotomy, as well as possible bruising and soreness at the phlebotomy site.

2.Twenty-four hour ambulatory blood pressure monitoring

The procedure may cause some mild discomfort during cuff inflation, but otherwise has no associated risk.

3.Ultrasonographic measurement of flow-mediated dilation (FMD) of the brachial artery

The procedure requires the subject to be supine for approximately 20 minutes. The inflation of the blood pressure cuff for 5 minutes may cause arm discomfort.

4.Risks associated with allopurinol

Allopurinol is a competitive xanthine oxidase inhibitor used as a urate-lowering agent in patients with gout and for secondary hyperuricemia associated with chemotherapy. The risks of therapy with allopurinol include cutaneous reactions, onset of gout, diarrhea, nausea, and elevation of alkaline phosphatase or transaminases. Most of these side effects are mild and reversible, but severe cutaneous reaction of the Stevens-Johnson type and bone marrow suppression, events that are reported in less than 1% of allopurinol recipients, may not be reversible.

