As stated above as the risks to pregnant women or an unborn baby when taking allopurinol are not fully known, women must have a pregnancy test before the study starts and again throughout the study. Women must not become pregnant during this study. Acceptable methods of birth control include hormonal control methods, inter-uterine device, a double-barrier method (diaphragm with spermicide, condom with spermicide) or abstinence.

If participants suspect that they may have become pregnant during the study, the study coordinator must contact the study PI immediately and instruct the participant to stop taking their study medication. If it is confirmed that the participant is pregnant, they will be withdrawn from the study. The study PI may want to schedule a follow up visit and may choose to follow the outcome of the pregnancy. Additionally, taking allopurinol may involve unknown risks to a nursing infant. If it is discovered that participants are breastfeeding, they are not eligible to participate in the study and their participation will be discontinued immediately.

The rate of AHS is estimated at 1/1000, and may be a particular concern for those with reduced renal function or carrying the HLA B5801 allele. We will expose 112 young adults with normal renal function to a dose of 300 mg per day of allopurinol as part of the study protocol, which include checking for the HLAB5801 allele in individuals of Han Chinese or Thai descent before exposure to allopurinol. Based on these rates of AHS and the procedures we have in place, we believe it is very unlikely, but possible that we could witness one severe cutaneous adverse reaction including AHS. Our stopping rule for safety re-evaluation would occur if we register more than one of such cutaneous adverse reaction (toxic epidermal necrolysis, Steven-Johnson's syndrome, AHS). We would then stop the study to comprehensively review safety and allopurinol dosing protocols. Other severe adverse reaction or deaths may or may not be related to the study drug and stopping or discontinuation of the study drug will be considered on an individual basis.

L. QUALITY and Safety ASSURANCE

1. Study team monitoring of data

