A database will be designed for the current study in the REDCap system. These computerized templates, are accessible through a secure web interface. Data entered into the system will be downloaded weekly and the database will have range and validity checks built in. All abnormal values will be flagged for further investigation. Research staff performing data entry will be trained in the use of the REDCap system and the study database. The study statistician will develop validity checks for outlier values, consistency, and completeness and will notify the principal investigator if issues are identified. Discrepancies will be adjudicated by consultation with the principal investigators. Once data entry is complete, the study data will be transferred to SAS statistical software and reviewed by the statistician.

16. Safety Monitoring and Reporting

The following defines the types of adverse events that study staff should inquire about at each visit. The type and possible causes of the adverse event will be discussed with the principal investigator, an examination will be conducted if deemed necessary, and it will be reported to the required parties. It is the responsibility of each and every study staff member to determine the appropriate line of action, to take the action agreed upon with the participant, and to subsequently report the event.

- Adverse Event (AE) - An AE is any unfavorable and unintended diagnosis, sign (including an abnormal laboratory finding), symptom, or disease temporarily associated with the study intervention, which may or may not be related to the intervention. AEs include any new events not present during the pre-intervention period or events that were present during the pre-intervention period which have increased in severity.

- Serious Adverse Event (SAE) - An SAE is any untoward medical occurrence that results is life-threatening, requires or prolongs hospitalization, causes persistent or significant disability/incapacity, results in congenital anomalies/birth defects, in death, or, in the opinion of the investigators, represents other significant hazards or potentially serious harm to research participants or others. All SAEs will be reported to the Safety officer (via KAI), Data Safety and Monitoring Board (DSMB), and IRB within 48 hours of the Principal Investigator becoming aware of the event.
- *Unexpected adverse event: Any adverse event, the specificity, frequency or severity of which is not consistent with either:*

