 - *the known or foreseeable risk of adverse events associated with the procedures involved in the research that are described in the protocol-related documents, such as the IRB-approved research protocol, any applicable investigator brochure, the current IRB-approved informed consent document, and other relevant sources of information, such as product labeling and package inserts; or*
 - *the expected natural progression of any underlying disease or condition of the participant(s) experiencing the adverse event.*

All AEs should be collected, analyzed, and monitored by using the serious adverse event form using the Adverse Event Reporting Form as well as the AE Tracking Log in the Research Electronic Data Capture system (REDCap). All laboratory abnormalities identified in the protocol as critical to participant safety must be reported. All AEs experienced by the participant from the time study drug administration through the end of the study are to be reported, as outlined in the protocol. The following delineates specific responsibilities of staff members:

- The research coordinator will complete the Adverse Event Form and AE Tracking Log in REDCap; assist the PI to notify the IRB, and Safety Officer of all the SAEs, and assist them to prepare SAE reports to IRB, and Safety Officer.
- The Principal Investigator will confirm that all AEs are correctly entered into the AE log with the study coordinator; be available to answer any questions that the coordinators may have concerning AEs; notify the IRB, FDA of all SAEs and AEs as appropriate.

The study coordinator will confirm that the AEs are correctly entered into the Adverse Event form and log in REDCap. They will confirm that the adverse events are reported to the appropriate regulatory bodies, as required. Additionally the project Safety Officer will receive safety tables every 12 weeks during the study period that include AE and SAE reports.

The proposed research meets the criteria of a clinical trial but it is not an NIH-Defined Phase III Clinical Trial since we propose to evaluate the mechanisms by which urate-lowering might contribute to blood pressure

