control and to compare its effects to placebo in 112 participants with prehypertension and stage I hypertension. [REDACTED] will be responsible for data safety and monitoring. As PIs they will complete and submit to the Project Advisory Committee monthly reports detailing the study progress and participant status, any adverse events, and any protocol deviations. Continuous, close monitoring of individual participant by the PIs will be assured throughout the study period. Events determined by the PIs to be serious, unanticipated problems involving risks, those not described in **Table 8. Adverse Events**, to the participants will be reported by the PIs to the IRB, DSMB, and the Safety Officer (via KAI) within 48 hours.

Table 8. Adverse Events – This document will be updated as needed.

Activities of Daily Living-ADL

Body Surface Area- BSA

Body System			
Cardiovascular	Mild	Moderate	Serious
Myocardial Infarction			All reported myocardial infarction will be classified as serious
Increased Blood Pressure	Systolic BP 140 - 159 mm Hg or diastolic BP 90 - 99 mm Hg; medical intervention indicated	Systolic BP \geq 160 mm Hg or diastolic BP \geq 100 mm Hg; medical intervention indicated	Life-threatening consequences (e.g., malignant hypertension, transient or permanent neurologic deficit, hypertensive crisis)
Hematology	Mild	Moderate	Serious
Anemia	13-10 Hb g/dl)	10-8 Hb g/dl	<8 Hb g/dl
Thrombocytopenia	150 000- 75 000/mm ³	<75,000 – 50,000/mm ³	<50,000 – 25,000/mm ³
Neutropenia	<LLN – 1500/mm ³	<1500-1000/mm ³	<1000-500/mm ³
Gastrointestinal	Mild	Moderate	Serious
Vomiting	1 - 2 episodes (separated by 5 minutes) in 24 hrs	3 - 5 episodes (separated by 5 minutes) in 24 hrs	\geq 6 episodes (separated by 5 minutes) in 24 hrs; tube feeding, TPN or hospitalization indicated
Diarrhea	Increase of <4 stools per day over baseline; mild increase in ostomy output compared to normal	Increase of 4 - 6 stools per day over baseline; moderate increase in ostomy output compared to normal	Increase of \geq 7 stools per day over baseline; incontinence; hospitalization indicated; serious increase in ostomy

Project 2: The Effects of Urate Lowering Therapy on Inflammation, Endothelial Function, and Blood Pressure (NIAMS: CORT)

			output compared to normal or death

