Other	Asymptomatic or mild symptoms; clinical or diagnostic observations only; intervention not indicated	Minimal, local or noninvasive intervention indicated; limiting age appropriate instrumental ADL	Medically significant or immediately life threatening; hospitalization or urgent intervention indicated
Musculoskeletal	Mild	Moderate	Serious
Joint pain	Mild pain	Moderate pain; limiting instrumental ADL	Serious pain; limiting self-care

Nervous	Mild	Moderate	Serious
Any patient reported event	Asymptomatic; clinical or diagnostic observations only; intervention not indicated	Moderate symptoms; limiting instrumental ADL	Serious symptoms; limiting self care ADL or death
Skin and subcutaneous tissue disorders	Mild	Moderate	Serious
Rash- characterized by a circumscribed and elevated skin lesion	Papules and/or pustules covering <10% BSA	Papules and/or pustules covering 10-30% BSA	Papules and/or pustules covering any % BSA, with life threatening consequences or death
Stevens Johnson Syndrome		Skin sloughing covering <10% BSA with associated signs (e.g., erythema, purpura, epidermal detachment and mucous membrane detachment)	Skin sloughing covering 10 - 30% BSA with associated signs (e.g., erythema, purpura, epidermal detachment and mucous membrane detachment) or death
Itch	Asymptomatic or mild symptoms; clinical or diagnostic observations only; intervention not indicated	Minimal, local or noninvasive intervention indicated	Medically significant or immediately life threatening; hospitalization or urgent intervention indicated

Hepatobiliary	Mild	Moderate	Serious
Abnormal liver enzymes	Above the upper limit to 2x ULN	2x ULN to 4X -	Greater than 4x ULN

Values and definitions derived from:

Common Terminology Criteria for Adverse Events (CTCAE) Version 4.0

Published: May 28, 2009 (v4.03: June 14, 2010) U.S. DEPARTMENT OF HEALTH AND HUMAN SERVICES

National Institutes of Health National Cancer Institute

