Type of AE	
Enter start date of AE	 Y-M-D
Enter stop date of AE	 Y-M-D
AE reported during which event?	
Skin and subcutaneous tissue	
Rash	<input type="text" value="MILD (papules and/or pustules, <10% BSA)"/>
How long did the rash last	
Location of rash	 Trunk  Face  Oral  Neck  Extremities  Palms/soles  Unknown
Current Fever?	 Yes  No reset
Patient Temperature (F)	
Were you taking Amoxicillin or Ampicillin at time of rash onset?	
Did you treat the rash?	 Yes  No reset
What was the treatment?	
Related to study?	
Action taken regarding study intervention?	
Serious Adverse Event?	 Yes  No reset
Stevens Johnson Syndrome	
SECOND ADVERSE EVENT	
Type of AE	
Enter start date of AE	 Y-M-D
Enter stop date of AE	 Y-M-D
AE reported during which event?	
Gastrointestinal	
Vomiting	
Related to study?	
Action taken regarding study intervention?	
Serious Adverse Event?	 Yes  No reset
Diarrhea	
THIRD ADVERSE EVENT	
Type of AE	
Enter start date of AE	 Y-M-D
Enter stop date of AE	 Y-M-D
AE reported during which event?	
Hepatobiliary	
Abnormal Liver Enzymes	

Screenshot 14 (continued). Adverse event report

FOURTH ADVERSE EVENT	
Type of AE	Musculoskeletal
Enter start date of AE	YYYY-MM-DD Today Y-M-D
Enter stop date of AE	YYYY-MM-DD Today Y-M-D
AE reported during which event?	
Musculoskeletal	
Joint Pain	
FIFTH ADVERSE EVENT	
Type of AE	Cardiovascular
Enter start date of AE	YYYY-MM-DD Today Y-M-D
Enter stop date of AE	YYYY-MM-DD Today Y-M-D
AE reported during which event?	

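### Table 8 grades Stevens-Johnson syndrome with under 10% skin sloughing as Moderate, although the protocol calls such reactions severe and counts any case toward the stopping rule (minor safety-reporting correction)

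*Combined protocol and SAP*

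**What the plan says.** - **Grade.** The SJS row of Table 8 (section 16) has an empty Mild cell. Its Moderate cell reads "Skin sloughing covering <10% BSA with associated signs". Its Serious cell covers 10–30% BSA, or death.
- **Risk description.** Section I.4 lists "severe cutaneous reaction of the Stevens-Johnson type and bone marrow suppression" among the harms that may not be reversible.
- **Stopping rule.** Section K names TEN, SJS and AHS. A stop for safety review "would occur if we register more than one of such cutaneous adverse reaction". It sets no threshold on BSA or grade.
- **A row graded by diagnosis.** The infarction row of Table 8 says "All reported myocardial infarction will be classified as serious".
- **SAE definition.** Section 16 lists outcomes (death, threat to life, hospitalization, disability, birth defect) and adds a judgment criterion: any event that, "in the opinion of the investigators, represents other significant hazards or potentially serious harm to research participants or others". SAEs go to the Safety Officer, DSMB and IRB within 48 hours. The definition in Appendix 3, SOP E, has the outcomes only.
- **Second 48-hour route.** Section 16 also covers "Events determined by the PIs to be serious, unanticipated problems involving risks, those not described in" Table 8.
- **Slower routes.** In section 16, "the project Safety Officer will receive safety tables every 12 weeks during the study period that include AE and SAE reports". Adverse events in general reach the IRB, DSMB and Safety Officer at continuing review, whose interval is not given.
- **Form.** The adverse event form (Appendix 2, Screenshot 14) has a separate yes/no field for "Serious Adverse Event".

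**The concern.** The protocol gives two different signals about the same event. Sections I.4 and K treat SJS as severe whatever its extent, and it is one of only three diagnoses that count toward the stopping rule. Table 8, the grading tool that staff use, calls the limited form Moderate next to a column headed Serious. The infarction row shows that the table can classify by diagnosis, but it does not do so for the reactions that the stopping rule is built on.

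What is at stake is how promptly independent overseers learn of a first case. The rule acts only at the second case, so early notice of the first is the useful safeguard. If a limited SJS case were not recorded as an SAE, no fixed expedited deadline to the DSMB or Safety Officer would apply.

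**Working it through.** The plan gives no figure of its own to reproduce here. The check sets the reporting rules side by side and adds short arithmetic for scale.

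**Step 1: can a first case reach the DSMB and Safety Officer within 48 hours?**

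| Route | Trigger | First SJS case under 10% BSA, not hospitalized or life-threatening |
|---|---|---|
| SAE, section 16 | Outcome, or investigator opinion | Only through opinion |
| SAE, Appendix 3 SOP E | Outcome only | Not covered |
| Unanticipated problem, section 16 | Serious, unanticipated, not described in Table 8 | Poor fit: SJS has a row in Table 8 and is foreseen in sections I.4 and K |

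TEN and AHS have no row in Table 8, but section K foresees both by name and section I.4 describes AHS. They are therefore hardly unanticipated, and they too depend on the SAE definition. No diagnosis-based rule makes any of the three an SAE. What is particular to SJS under 10% BSA is the Moderate label.

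**Step 2: what remains if the case is not judged an SAE?** The fixed routes to these two overseers are the 12-week tables to the Safety Officer, 12 × 7 = 84 days at most against 2 days, and continuing review for the DSMB, at an unstated interval.

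**Step 3: how likely is any such reaction?** Inputs: 112 exposed (section K); 1 per 1000 patients (section K; section I.4 says fewer than this); 0.69 per 1000 person-years (section I.4). I assume independent cases and, for the second rate, 28 days of exposure each and a constant hazard.

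- At 1/1000: P(at least one) = 1 − 0.999^112 = 0.106. P(two or more) = 0.106 − 112 × 0.001 × 0.999^111 = 0.0058.
- At 0.69 per 1000 person-years: 112 × 28 / 365.25 = 8.59 person-years. Expected events = 8.59 × 0.00069 = 0.0059. P(at least one) = 1 − exp(−0.0059) = 0.0059.

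At the first rate, P(exactly one, given at least one) = 1 − 0.0058 / 0.106 = 0.945. If a reaction occurs, it will most likely be a single one, which the stopping rule alone does not act on.

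These probabilities cover all such severe reactions, not only SJS under 10% BSA. The chance of a late report is smaller and cannot be computed from the documents.

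**The case against.** The strongest reply is that a late report requires investigators to contradict their own protocol. Table 8 does not decide SAE status. The section 16 definition does, and the form records it in its own field. The same team calls these reactions severe and made them stopping events, so it would have to judge a confirmed SJS case to carry no potential for serious harm. Nearly every diagnosis in the plan rests on outcome or judgment, and infarction is the only event-level row made serious by name.

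Other routes also exist. Table 6 has PIs told of any adverse event within 24 hours. The communications plan (section 4) expects severe events, or those needing further review, to have been reported at once. SOP E sends any adverse event to the sponsor and IRB within 10 working days. Section L.2 gives monthly reports to the Project Advisory Committee and regular reports to the Safety Officer, and lets the PI or Chair call an emergency DSMB meeting.

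Most of this stands, and it makes the point minor. It does not remove the point. None of these routes gives the DSMB or Safety Officer a fixed prompt deadline, SOP E lacks the judgment criterion on which the reply relies, and the label still conflicts with sections I.4 and K.

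A reader might infer more than the documents support:

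- *That about seven more participants would be put at risk by late notice.* At 30 enrolments per year, 30 × 84 / 365.25 = 6.9 could enrol in 84 days. But no documented action pauses enrolment after one case, even one reported in 48 hours, so the figure measures no harm.
- *That TEN and AHS are safe because they can use the unanticipated-problem route.* They are foreseen in the protocol and fit it poorly. An event judged serious enough for that route would normally already qualify under the SAE definition.
- *That the ungraded ranges are a safety defect.* Platelets below 25,000, neutrophils below 500, non-fatal SJS above 30% BSA and non-life-threatening rash above 30% BSA have no grade. No safety action in the documents depends on them.

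**Conclusion.** The point holds as a minor safety-reporting correction. The Moderate grade for SJS under 10% BSA conflicts with the protocol's own description of the reaction and with its place in the stopping rule. For SJS, TEN and AHS alike, expedited notice of a first case rests on outcome or opinion, and SOP E omits opinion.

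The practical effect is small. A severe cutaneous reaction of any kind has a probability of roughly 0.6% to 10.6% over the trial at the two rates given, under the assumptions above. A late report also needs a limited case and an unlikely judgment. The outer limit for fixed notice to the Safety Officer is 84 days instead of 2, ignoring the less formal routes. The documents do not support reading this as a flaw in the stopping rule, which counts by diagnosis and is untouched by the grade. Sample size, power and analysis are not affected.

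**What to change.** - Replace the SJS row of Table 8 with one modelled on the infarction row: every reported case of SJS, TEN or AHS is serious. Leave its Moderate cell empty.
- Add one sentence to section 16 and to SOP E: any of the three is an SAE, reported within 48 hours whatever the BSA involved.
- Check the adverse event form and change its labels only where they differ. The SJS list is not expanded in Screenshot 14, so its options cannot be seen.
- Optional tidying: make the Serious cells open-ended (platelets below 50,000, neutrophils below 1000) and add rash above 30% BSA.

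The required cost is one table row and one sentence in each of two places, plus at most a rare extra expedited report. Visits, data collected, sample size and the stopping rule stay as they are. Section 16 already provides for Table 8 to be updated.

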Appendix 2- Study Forms and Screenshots from the REDCap System

Screen shots from the REDCap System

Project 2: The Effects of Urate Lowering Therapy on Inflammation, Endothelial Function, and Blood Pressure (NIAMS: CORT)

1. Prescreening call #1 – Eligibility criteria
2. Prescreening call #2 – Contact information
3. Screening visit #1 – Blood pressure measurement
4. Screening visit #2 – Medical history, sample collection and pill distribution
5. Screening visit #3 – Laboratory results
6. Phone Check-in #1
7. Phone Check-in #2
8. Visits 2, 3, 5 #1 – Pill count, adverse event check, and physical exam
9. Visit 4 #1 – Adverse event check and physical exam
10. Visit 2-5 #2 – Current medical conditions and medications, blood pressure measurement
11. Visit 2-5 #3 – Sample collection and laboratory results
12. Visit 2-5 #4 – Flow-mediated dilation
13. Between visits phone check-in
14. Adverse event report
15. Study completion

Following the screening visit (visit 1) the screen shots for study visits 2-5 repeat in the system.

Appendix 2

Screenshot 1. Prescreening call #1 – Eligibility criteria

Event Name: SCREEN: Pre-Screening Call	
Record ID Field	888
Study Subject Initials	
Study ID/Number	
Date of screening	 Today Y-M-D
Date of birth	 Today Y-M-D
Age (years)	 View equation
Gender	 Female  Male
Do you have a history of gout?	 Yes  No
Have you ever been diagnosed with diabetes?	 Yes  No
Are you taking a medicine for your blood pressure?	 Yes  No
Are you taking a medicine that lowers your uric acid for a condition such as gout?	 Yes  No
Which uric acid lowering medicine?	
Are you taking a medicine for your cholesterol?	 Yes  No
Which medicine for cholesterol?	
Any serious medical conditions?	 Yes  No
Description of serious medical condition:	
Are you taking Prednisone or a steroid medicine?	 Yes  No
Are you on a medicine called azathioprine (Imuran)?	 Yes  No
Are you currently pregnant or have you delivered a baby or had a miscarriage (terminated a pregnancy) in the last 3 months?	 Yes  No
Have you had a regular monthly cycle for the last 3 months?	 Yes  No
Have you ever smoked?	 Yes  No
Do you currently smoke?	 Yes  No
When did you quit smoking?	 > 3 months ago  <= 3 months ago
Do you currently work night shift?	 Yes  No
Are you able to earn income in the US?	 Yes  No
Race	
Do you consider yourself to be Hispanic or Latino?	 Yes  No
How did you hear about the study?	
NOT ELIGIBLE TO CONTINUE	

Appendix 2

Screenshot 2. Prescreening call #2 – Contact information

Event Name: SCREEN: Pre-Screening Call	
Record ID Field	888
Participant Contact	
First Name	
Middle Initial	
Last Name	
Address1	
Address2	
City	
State	
Zip	
Telephone	
Email	
Primary Contact	
First Name	
Last Name	
Address1	
Address2	
City	
State	
Zip	
Telephone	
Email	
Is this a 24-hour medical contact?	 Yes  No reset
Secondary Contact	
First Name	
Last Name	
Address1	
Address2	
City	
State	
Zip	
Telephone	
Email	
Is this a 24-hour medical contact?	 Yes  No reset
REMINDER: Go to scheduling page/calendar to schedule/confirm date of appointment	

Appendix 2

Screenshot 3. Screening visit #1 – Blood pressure measurement

Event Name: SCREEN: Visit	
Record ID Field	888
Date of Screening visit	 Today Y-M-D YYYY-MM-DD
Obtained Written Informed Consent?	 Yes  No reset
Upload Consent Form	Upload document
Blood Pressure	
After sitting quietly for 10 minutes, simultaneous BP measurement in both arms using Omron automated sphygmomanometer. In parallel 30 seconds apart between arms.	
Right Upper arm circumference (in cm)	
Left Upper arm circumference (in cm)	
Cuff Size	
Blood Pressure 1	
Time - 1st Blood Pressure measurement	 Now H:M
1st measure - SBP (mm Hg) - right arm	
1st measure - DBP (mm Hg) - right arm	
1st measure - SBP (mm Hg) - left arm	
1st measure - DBP (mm Hg) - left arm	
Blood Pressure 2	
Time - 2nd Blood Pressure measurement	 Now H:M
2nd measure - SBP (mm Hg)	
2nd measure - DBP (mm Hg)	
Blood Pressure 3	
Time - 3rd Blood Pressure measurement	 Now H:M
3rd measure - SBP (mm Hg)	
3rd measure - DBP (mm Hg)	
Mean SBP	 View equation
Mean DBP	 View equation
NOT ELIGIBLE TO CONTINUE	

Screenshot 4. Screening visit #2 – Medical history, sample collection and pill distribution

Event Name: SCREEN: Visit	
Record ID Field	888
Gynecological	
Do you have a regular menstrual cycle?	 Yes  No reset
When was your last menstrual cycle?	   Today Y-M-D
Are you on any hormonal birth control?	 Yes  No reset
If NO, date subject stopped:	
Birth control method:	
Important Medications	
Medication 1	
Anthropometric	
Weight (pounds)	
Height (inches)	
BMI	 View equation
Hip Circumference (cm) - measure at femoral trochanter	
Waist Circumference (cm) - measure at umbilicus	
PHYSICAL EXAM	
Physical Exam Performed By:	
Skin	 Normal  Abnormal reset
Musculoskeletal	 Normal  Abnormal reset
HEENT	 Normal  Abnormal reset
Abdomen	 Normal  Abnormal reset
Heart / Lung	 Normal  Abnormal reset
Neuro	 Normal  Abnormal reset
Family Medical History	
Gout	 Yes  No reset
Comments	
Hypertension	 Yes  No reset
Angina/Myocardial Infarction	 Yes  No reset
Stroke	 Yes  No reset
Diabetes	 Yes  No reset
Other	 Yes  No reset
Sample Collection	
Blood sample drawn (Red top, purple top, green top)	 Yes  No reset
Urine sample collected?	 Yes  No reset
Pill Distribution	
Patient eligible for 2-week run-in period?	 Yes  No reset
Pill bottle serial number	
Number of pills given	
REMINDER: Go to scheduling page/calendar to schedule/confirm date of appointment	

Screenshot 5. Screening visit #3 – Laboratory results

Event Name: SCREEN: Visit	
Record ID Field	888
Medical Record Number	
Pregnancy test	 Negative  Positive reset
Cotinine test	 Negative  Positive reset
Alkaline Phosphatase (39-117 Units/L)	
AST (14-40 Units/L)	
ALT (10-44 Units/L)	
Hemoglobin (12-15 g/dL)	
WBC (4000-11,000)	
Platelet count (150,000-400,000)	
Serum Uric Acid (2.0-6.9 mg/dl)	
Serum Creatinine (0.4-1.2 mg/dL)	
Estimated Glomerular filtration rate (ml/min)	 View equation
NOT ELIGIBLE TO CONTINUE	

Appendix 2

Screenshot 6. Phone Check-in #1

Event Name: SCREEN: Phone check-in A	
Record ID Field	888
Enrollment confirmed	 Yes  No reset
Menstrual cycle information	
Date of Visit 1	  Y-M-D YYYY-MM-DD
Form Status	
Complete?	
 	
	

Screenshot 7. Phone Check-in #2

Event Name: SCREEN: Phone check-in B	
Record ID Field	888
Started menstrual cycle?	 Yes  No reset
Call Again Tomorrow	
Started menstrual cycle?	 Yes  No reset
New Visit Date	  Y-M-D YMD
ADVERSE EVENTS?	
Does patient report any Adverse Events?	 Yes  No reset
REMEMBER: Fill out AE Report	

Appendix 2

Screenshot 8. Visits 2, 3, 5 #1 – Pill count, adverse event check, and physical exam

Record ID Field	888
Patient ID confirmed	 Yes  No
Date of today's visit	 Today Y-M-D
Date of last visit	 Today Y-M-D
Pills given at last visit	
Current pill count	
Compliance %	 View equation
Within first 7 days of menstrual cycle?	 Yes  No
ADVERSE EVENTS?	
Does patient report any Adverse Events?	 Yes  No
REMEMBER: Fill out AE Report	
Physical Exam Required?	 Yes  No
PHYSICAL EXAM	
Physical Exam Performed By:	
Skin	 Normal  Abnormal  NA
Rash	
Other Skin?	
Musculoskeletal	 Normal  Abnormal  NA
Joint Pain	 Yes  No
Number of joints involved	
Type of joint (select all that apply)	 Shoulder  Elbow  Wrist  MCP  PIP/DIP  Hip  Knee  Ankle  MTP
Redness?	 Yes  No
Swelling?	 Yes  No
Comments	
Other Musculoskeletal?	
HEENT	 Normal  Abnormal  NA
Abdomen	 Normal  Abnormal  NA
Heart / Lung	 Normal  Abnormal  NA
Neuro	 Normal  Abnormal  NA

Appendix 2

Screenshot 9. Visit 4 #1 – Adverse event check and physical exam

Record ID Field	888
Patient ID confirmed	 Yes  No reset
Date of today's visit	 YMD  Y-M-D
ADVERSE EVENTS?	
Does patient report any Adverse Events?	 Yes  No reset
REMEMBER: Fill out AE Report	
Physical Exam Required?	 Yes  No reset
PHYSICAL EXAM	
Physical Exam Performed By:	
Skin	 Normal  Abnormal  NA reset
Rash	
Other Skin?	
Musculoskeletal	 Normal  Abnormal  NA reset
Joint Pain	 Yes  No reset
Other Musculoskeletal?	
HEENT	 Normal  Abnormal  NA reset
Abdomen	 Normal  Abnormal  NA reset
Heart / Lung	 Normal  Abnormal  NA reset
Neuro	 Normal  Abnormal  NA reset

Screenshot 10. Visit 2-5 #2 – Current medical conditions and medications, blood pressure measurement

Record ID Field	888
UPDATED MEDICAL HISTORY	
Current Medical Conditions	
Diagnosis	
Treatment	
Status/Comments	
Diagnosis	
Medications	
List all the medications that the patient is taking or has taken in the past 28 days. (Include nutritional supplements, herbal/alternative medicines)	
Medication	
BLOOD PRESSURE	
Blood Pressure	
Using standard Omron automated sphygmomanometer on the LEFT arm. All measurements should be made using the same cuff size and equipment after 15 minutes of sitting quietly. Take each reading 3 minutes apart.	
Time - 1st Blood Pressure measurement	  H:M
BP1 - Sitting pulse	
1st measure - SBP (mm Hg)	
1st measure - DBP (mm Hg)	
Blood Pressure 2	
Time - 2nd Blood Pressure measurement	  H:M
BP2 - Sitting pulse	
2nd measure - SBP (mm Hg)	
2nd measure - DBP (mm Hg)	
Blood Pressure 3	
Time - 3rd Blood Pressure measurement	  H:M
BP3 - Sitting pulse	
3rd measure - SBP (mm Hg)	
3rd measure - DBP (mm Hg)	
Mean SBP	 View equation
Mean DBP	 View equation

Screenshot 11. Visit 2-5 #3 – Sample collection and laboratory results

Record ID Field	888
VISIT LABS	
Blood drawn (red top, 2 purple tops, green top, SST)	 Yes  No
Blood draw - time	
Sample Tube ID	
Sent to Lab	 Yes  No
Sent to Lab - time	
Urine collected	 Yes  No
Urine collection - time	
Sample Tube ID	
Sent to Lab	 Yes  No
Sent to Lab - time	
Sample sent for serum banking (purple top, SST)	 Yes  No
Serum bank - time	
Pregnancy test	 Negative  Positive
Continine test	 Negative  Positive
Scheduled Date (from calendar)	 Today Y-M-D <small>YYYY-MM-DD</small>
Lab Results	
Alkaline Phosphatase (39-117 Units/L)	
AST (14-40 Units/L)	
ALT (10-44 Units/L)	
Hemoglobin (12-15 g/dL)	
WBC (4000-11,000)	
Platelet count (150,000-400,000)	
Serum Uric Acid (2.0-6.9 mg/dl)	
Serum Creatinine (0.4-1.2 mg/dL)	
Estimated Glomerular filtration rate (ml/min)	 View equation
Highly Sensitive C-Reactive Protein (mg/L)	

Screenshot 12. Visit 2-5 #4 – Flow-mediated dilation

Record ID Field	888
FLOW-MEDIATED DILATION (FMD)	
Performed by	
Assistant	
Start time	
End Time	
Initial blood pressure - SBP (mm Hg)	
Initial blood pressure - DBP (mm Hg)	
Initial heart rate (bpm)	
Cuff inflated 50 mmHg above systolic to: (mm Hg)	
Baseline 1 min	
Start Recording	
End Recording	
Inflation	
Deflation	
Start Recording	
End Recording	
Additional FMD	
FMD BL absolute (cm)	
# of BL readings	
SD	
BL flow (cm/sec)	
Hyperemic flow velocity (cm/sec)	
FMD post cuff release (cm)	
SD	
FMD%	 View equation
FMD corrected for shear stress: FMD/hyperemic flow velocity (100*sec/cm)	 View equation
BL flow (cm/sec)	
Hyperemic flow velocity (cm/sec)	
FMD post cuff release (cm)	
SD	
FMD%	 View equation
FMD corrected for shear stress: FMD/hyperemic flow velocity (100*sec/cm)	 View equation
FMD Comments:	
Expand	
OPTIONAL: Blood Pressure Monitor	
Blood pressure monitor given to patient?	 Yes  No
Patient Randomization ID:	 reset
<small>* must provide value</small>	

Screenshot 13. Between visits phone check-in

Record ID Field	888
Patient Study ID	
Pills given at last visit	
Current pill count	
Compliance %	 View equation
ADVERSE EVENTS?	
Does patient report any Adverse Events?	 Yes  No reset
REMEMBER: Fill out AE Report	
Any new medication begun?	 Yes  No reset
Comments	

 Expand
Next scheduled visit	  Y-M-D
Form Status	
Complete?	
  	

Screenshot 14. Adverse event report

Event Name: ADVERSE EVENTS	
Record ID Field	888
ADVERSE EVENT REPORT	
No Adverse Events To Date	 None Reported
FIRST ADVERSE EVENT	
Type of AE	
Enter start date of AE	 Y-M-D
Enter stop date of AE	 Y-M-D
AE reported during which event?	
Skin and subcutaneous tissue	
Rash	<input type="text" value="MILD (papules and/or pustules, <10% BSA)"/>
How long did the rash last	
Location of rash	 Trunk  Face  Oral  Neck  Extremities  Palms/soles  Unknown
Current Fever?	 Yes  No reset
Patient Temperature (F)	
Were you taking Amoxicillin or Ampicillin at time of rash onset?	
Did you treat the rash?	 Yes  No reset
What was the treatment?	
Related to study?	
Action taken regarding study intervention?	
Serious Adverse Event?	 Yes  No reset
Stevens Johnson Syndrome	
SECOND ADVERSE EVENT	
Type of AE	
Enter start date of AE	 Y-M-D
Enter stop date of AE	 Y-M-D
AE reported during which event?	
Gastrointestinal	
Vomiting	
Related to study?	
Action taken regarding study intervention?	
Serious Adverse Event?	 Yes  No reset
Diarrhea	
THIRD ADVERSE EVENT	
Type of AE	
Enter start date of AE	 Y-M-D
Enter stop date of AE	 Y-M-D
AE reported during which event?	
Hepatobiliary	
Abnormal Liver Enzymes	

Screenshot 14 (continued). Adverse event report

FOURTH ADVERSE EVENT	
Type of AE	Musculoskeletal
Enter start date of AE	YYYY-MM-DD Today Y-M-D
Enter stop date of AE	YYYY-MM-DD Today Y-M-D
AE reported during which event?	
Musculoskeletal	
Joint Pain	
FIFTH ADVERSE EVENT	
Type of AE	Cardiovascular
Enter start date of AE	YYYY-MM-DD Today Y-M-D
Enter stop date of AE	YYYY-MM-DD Today Y-M-D
AE reported during which event?	
Cardiovascular	
Myocardial infarction	
Increased Blood Pressure?	
SIXTH ADVERSE EVENT	
Type of AE	Hematology
Enter start date of AE	YYYY-MM-DD Today Y-M-D
Enter stop date of AE	YYYY-MM-DD Today Y-M-D
AE reported during which event?	
Hematology	
Anemia	
Thrombocytopenia	
Neutropenia	
SEVENTH ADVERSE EVENT	
Type of AE	Nervous System
Enter start date of AE	YYYY-MM-DD Today Y-M-D
Enter stop date of AE	YYYY-MM-DD Today Y-M-D
AE reported during which event?	
Nervous	
Any patient reported event	
EIGHTH ADVERSE EVENT	
Type of AE	Hepatobiliary
Enter start date of AE	YYYY-MM-DD Today Y-M-D
Enter stop date of AE	YYYY-MM-DD Today Y-M-D
AE reported during which event?	
Hepatobiliary	
Abnormal Liver Enzymes	

Appendix 2

Screenshot 15. Study completion

Record ID Field	888
Date of final visit	  Today Y-M-D
Primary reason for terminating participation in study	
Comments	

 Expand
Form Status	
Complete?	
  	

